Study Title: Storytelling Narrative Communication Intervention for Smoking Cessation in Women Living with HIV

NCT Number: NCT03289676

Date: 01/10/2018

University of Massachusetts Boston Institutional Review Board Protocol

A. Title: Storytelling Narrative Communication Intervention for Smoking Cessation in Women Living with HIV

B. Investigators: [name], RN, University of Massachusetts Boston
 [name], RN, FAAN, Dana-Farber/Harvard Cancer Center
 [name], RN, APHN-BC, FAAN, University of Massachusetts Boston

PROJECT DESCRIPTION

HIV has transformed into a chronic illness due to the advent of effective treatments in the absence of a cure. As a result, the prevalence of non-AIDS defining cancers (NADCs), including lung cancer, has increased three-fold among people living with HIV. NADCs now account for 50% of all cancers among the people. Smoking is one of the major contributing factors to lung cancer and smoking prevalence is substantially higher in this population than the general U.S. population. Smoking prevalence does not differ by gender among people living with HIV. Women of color, particularly African American women represent the majority of women living with HIV (WLHIV) followed by Latinas. WLHIV smoke at a rate almost 3 times higher than that for the general U.S. female population (e.g., 42% vs. 16%). The proposed study has two phases: 1) the development of a storytelling narrative communication (SNC) intervention that will be added to an established HIV-tailored smoking cessation intervention and 2) a two-arm randomized controlled trial (RCT) of the HIV-tailored intervention plus the SNC Intervention compared with the HIV-tailored intervention only. We will develop narrative videos with three to five WLHIV who will be talking about their personal struggles with smoking and success in quitting. Our preliminary study revealed that the established HIV-tailored intervention was effective only for short-term (≤ 2 months) abstinence. Many relapsed to smoking between the 2nd and 6th month of quitting. We propose that the SNC intervention will be an effective strategy to sustain their quit efforts for long-term abstinence (≥ 6 months). A total of 60 WLHIV will be recruited and randomly assigned to either the experimental arm (a combination of HIV-tailored and SNC interventions) or the control arm (HIV-tailored intervention only).

STUDY AIMS

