The Purposes of the study are to 1) Identify SNC intervention components that are rated high in transport and identification for use as an enhancement to an HIV-tailored smoking cessation intervention; 2) Determine the feasibility and acceptability of the SNC intervention for WLHIV by assessing the rate of recruitment and retention for feasibility and the degree of transport and identification for acceptability; and 3) Establish an effect size of HIV-tailored and SNC interventions for smoking cessation in comparison with the HIV-tailored smoking cessation intervention only for WLHIV, for subsequent grant applications.

SIGNIFICANCE OF THE STUDY

People living with HIV now live longer because of the use of highly active antiretroviral therapy.¹⁻³ However, the burden of non-AIDS related, especially, non-AIDS defining cancers (NADCs) has increased considerably and smoking is a profound cause of NADCs.³⁻⁶ These cancers now account for 50% of all cancers among those with HIV, with lung cancer being the most common and deadliest cancer.⁶ People living with HIV smoke cigarettes at much higher rates than the general U.S. population i.e., 40-80% versus 19%.^{1,7-9} There is no gender difference in smoking prevalence among people living with HIV. Women living with HIV (WLHIV) smoke at a rate almost three times higher than that for the general U.S. female population.⁹ Given the strong association between smoking and the development of lung cancer, smoking cessation interventions that are tailored to the group are critical to decrease the morbidity and mortality associated with lung cancer.

Women of color, particularly, African American women in the United States represent the majority of WLHIV followed by Latinas.¹⁰ Blacks bear a disproportionate share of cancer burden, having the highest death rate and shortest survival of any racial or ethnic group for most cancers.¹¹⁻¹³ Five-year relative survival is lower for Blacks than for Whites in most cancers at each stage of diagnosis.¹¹ The majority of participants in smoking

cessation studies for people living with HIV were males (> 80%) and studies conducted with WLHIV are very scarce.¹⁴ Compared to men, women face more barriers to seeking treatment, including transportation and childcare issues.¹⁵ A smoking cessation intervention that can be accessible at home may be an alternative strategies to reach WLHIV.

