- Phase 1. Development of Narrative Video:** We will first develop narrative videos in collaboration with community organizations of WLHIV in Boston. The video will be filmed in person at the University of Massachusetts Boston.
- Phase 2. A Randomized Controlled Trial (RCT) of a Story Telling Narrative Communication Intervention:** We will conduct a two-arm RCT assigning participants at a ratio of 1:1 to either one of the two arms (**Experimental:** HIV-tailored plus SNC interventions vs. **Control:** HIV-tailored plus attention-control interventions). Both arms will have eight weekly sessions of a 30-minute HIV-tailored cessation intervention (cognitive behavioral therapy plus nicotine patches). The experimental arm will receive three 5-minute SNC videos (testimonial stories about successful quitting), each per month between the first and third month of quitting, whereas the control arm receive three 5-minute attention control videos (women talking about being diagnosed with HIV) at the same monthly interval. However, participants in the control arm will also receive the SNC videos talking about successful stories of smoking cessation right after the last follow-up assessment (3-month follow-up post-quit). The overall flow of the study is illustrated in Figure 1. All research-related procedures will be conducted remotely.

Figure 1. The overall design of the study

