Nicotine replacement therapy. Participants in both arms will receive a free supply of nicotine patches (Habitrol Patches, Novartis, Denmark) via post office mail at two separate occasions: first 4-week supplies of 21mg and then 2-week supplies of each 14mg and 7mg together. Those who smoke between 5-9 cigarettes will receive 14mg for 6 weeks and then 7mg for 2 weeks. Those who report difficulty using patches due to skin reactions and who earn a high score (≥ 7) on the Fagerstrom Test for Nicotine Dependence^{38,39} will receive nicotine gums (2 or 4mg, Habitrol Gums, Novartis, Denmark). Adherence to nicotine patches and gums will be monitored asking number of patches and gums that they have used for the past 7 days. Prior to receiving nicotine patches and gums, participants will be instructed as to correct usage and possible side effects of the products, and which side effects that they should report immediately. Nicotine replacement products will be used in the study in accordance with their FDA approved labeling.

Video Watching. Participants in both arm will be randomly assigned to either the SNC or attention-control interventions and accordingly receive the videos of either quitting smoking or being diagnosed with HIV infection, respectively. Participants in the control arm will also receive the SNC videos of quitting smoking right after the last data collection that is 3-month follow-up post-quit.

Saliva Cotinine Test. Participant who report abstinence at 3-month follow-up will receive two NicAlert™ test kits in 2-3 days via express mail. They will conduct the test at home and hence, there is no transportation of samples. Research staff will inform that participants should not open sealed test strips before the test. She/he will also inform them that they should not eat or drink for at least 30 minutes before the test. The staff person will assist them in testing by providing following step-by-step instructions.

1. Take out collection tube and funnel from the white vinyl bag.
2. Put the funnel in a collection tube.
3. Spit into the collection tube through the funnel until the tube is half full.
4. Discard the funnel and close the tube with a cap until you hear click.
5. Tear off the sealed white wrap and take out the test strip inside
6. Put the strip on the flat surface.
7. Squeeze the collection tube while holding it upside down

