Specific Aim 2: Determine the feasibility and acceptability of an SNC intervention for smoking cessation for WLHIV by assessing 1) the rate of **recruitment and retention** for feasibility and 2) the degree of **transport and identification** for acceptability in the narrative enhancement. We will identify and describe the time to recruitment and any barriers. We will also describe reasons for study refusal and compare refusal rates by age ranges and number of cigarettes smoked per day, using χ^2 and t-tests. We will compare attrition rates at each follow-up by intervention condition and abstinence status, using Mann-Whitney tests. Subjects will complete an Exit Survey, rating their overall satisfaction with the intervention that they have. They will also rate their experience with the SNC videos, using a 7-point Likert-type scale.⁴⁵ In addition, the Measure of Narrative Engagement will be used as a quantitative indicator of 1) narrative understanding, 2) attentional focus, 3) narrative presence, and 4) emotional engagement.¹⁹

Specific Aim 3: Establish an effect size of HIV-tailored smoking cessation and SNC interventions in comparison with the HIV-tailored smoking cessation intervention only for WLHIV by comparing 30-day abstinence rates at 6-month follow-up. We will evaluate the balance of baseline demographics and smoking behavior between the two arms, using t-tests or Mann-Whitney tests for continuous variables and χ^2 tests for categorical variables. We will examine differences in continuous or 7-day point-prevalence abstinence rates between the two arms, using the χ^2 tests. Individuals who are not available at follow-up assessments or yield a cotinine test result higher than the cutoff level of 0 (cotinine level 0-30mg/ml) will be all treated as smoking. We will calculate an effect size by comparing 30-day abstinence rates at 6-month follow-up point between the two arms. We will also explore longitudinal logistic regression models under the framework of generalized linear mixed models to examine the relationships between abstinence status and intervention conditions over time.

PROTECTION OF HUMAN SUBJECTS

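### Control women receive the SNC videos right after month 3, but Aim 3 takes its effect size at month 6, which is unscheduled and would compare early with delayed SNC

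*Protocol*

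**What the plan says.** **Video schedule.** Under Research Design, Phase 2, the experimental arm gets three SNC videos, "each per month between the first and third month of quitting". The control arm gets attention-control videos at the same interval. The same paragraph then says that "participants in the control arm will also receive the SNC videos talking about successful stories of smoking cessation right after the last follow-up assessment", which it places at 3 months post-quit, and Study Procedures, Video Watching repeats it: "Participants in the control arm will also receive the SNC videos of quitting smoking right after the last data collection that is 3-month follow-up post-quit".

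**Effect size.** Data Analysis, Specific Aim 3 reads, identically in Protocol and SAP: "We will calculate an effect size by comparing 30-day abstinence rates at 6-month follow-up point between the two arms". Purpose 3 under Study Aims sets the comparator: the effect size is to be established "in comparison with the HIV-tailored smoking cessation intervention only for WLHIV". The Project Description places the expected benefit at 6 months or longer.

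**Follow-up.** Study Procedures, Phase 2 lists follow-up at post-quit months 1, 2 and 3. Study Measures and Assessment Procedures counts three follow-up assessments, and Table 1 stops at month 3. No 6-month contact appears.

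**The concern.** The randomised contrast has two different end points. The design and procedures sections close it at month 3, when controls are given the active component. Aim 3 reads it at month 6.

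The obvious repair for the missing 6-month visit is to add one. Done alone, that would not rescue Aim 3, because the control arm would by then have had the SNC videos for about three months and would no longer be the HIV-tailored-only comparator named in the Study Aims.

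The Study Aims say that the effect size is meant for later grant applications. A diluted difference carried forward could make a useful intervention look weak and would distort the size of the next trial.

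**Working it through.** **1. Can month 6 be read before release?** Release is at 3 months post-quit. Six months post-quit is three months later. If month 6 were counted from baseline, the quit day is usually set between the third and fifth weekly sessions (Individual counseling before the quit day), so the reading would still fall about 5 months post-quit. On either count it follows release.

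**2. The plan's own sample size.** Inputs from Power and Sample Size: p1 = 0.455, p2 = 0.20, two-sided 5%, 80% power. With p̄ = (p1 + p2)/2 = 0.3275 and d = 0.255:

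n per arm = [1.960·√(2p̄(1 − p̄)) + 0.842·√(p1(1 − p1) + p2(1 − p2))]² / d²

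= [1.960·√0.4405 + 0.842·√0.4080]² / 0.0650 = 51.97, rounded up to 52. The stated figure is reproduced, so there is no error in it.

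**3. Illustration of dilution.** Let f be the share of the SNC effect that controls gain between release and a month-6 reading. The documents give no value for f, so it is an assumption shown over a range. Two further assumptions are that 45.5% and 20% can stand in as undiluted month-6 rates (the 20% is a 3-month rate in the plan, and the 45.5% has no stated time point), and that the experimental rate does not change.

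Control rate = 20 + f × 25.5, and difference = 25.5 × (1 − f), in percentage points:

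| f | Control rate | Difference (points) | Loss (points) | n per arm, 80% power |
|---|---|---|---|---|
| 0 | 20.0% | 25.5 | 0 | 52 |
| 0.10 | 22.6% | 23.0 | 2.6 | 66 |
| 0.25 | 26.4% | 19.1 | 6.4 | 98 |
| 0.50 | 32.8% | 12.8 | 12.8 | 229 |

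**4. Against sampling error.** At the planned 25 per arm and f = 0, the standard error of the difference is √(0.4080/25) = 0.128, or 12.8 points. The loss is about half a standard error at f = 0.25 (6.4/12.8) and about one at f = 0.50.

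**5. What is not touched.** Assessments at months 1, 2 and 3 precede release, so arm comparisons at those times, and a longitudinal model fitted to them, still contrast SNC with no SNC.

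**The case against.** The strongest reply is that nothing is contaminated, because no month-6 data will exist. Release is tied to the last assessment, which is ordinary delayed access for controls, and the only slip is that Aim 3 names an unscheduled time point. Much of this stands: moving Aim 3 to month 3 cures the problem without changing the release rule. What remains is that the current text points to month 6 in both the hypothesis and the effect size, and adding that visit alone would leave the contrast wrong.

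A reader might infer that the month-6 comparison is certainly biased toward no effect. The documents do not support that. Dilution requires the videos to help women who first see them after month 3, whereas the plan delivers them in months 1 to 3 of quitting and describes them as sustaining abstinence. At the plan's 20% rate, 80% of controls are smoking at month 3. If none of the abstinent 20% relapsed and the whole gain came from the smokers, f = 0.50 would need 12.75/80, about 16%, to become abstinent again, and f = 0.25 would need 6.375/80, about 8%. The larger values of f are therefore strong assumptions.

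A reader might also infer that the videos reach controls before the month-3 cotinine test. The Saliva Cotinine Test section does have kits arriving 2 to 3 days after abstinence is reported. However, Study Measures and Assessment Procedures mails them just before the assessment, Table 1 lists the test as a month-3 measure, and Video Watching places release after the last data collection, which can naturally include the test. Only women who have already reported abstinence are tested. This is a point to clarify and does not show contamination.

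**Conclusion.** The conflict is explicit and stands on the text alone: control release at month 3 is incompatible with an Aim 3 effect size at month 6 against an HIV-tailored-only comparator. As scheduled, the month-6 contrast cannot be collected. If it were collected under the present release rule, it would compare early with delayed SNC.

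The direction of any dilution is conditional and its size is unknown. The drop from 25.5 to about 23, 19 or 13 points rests on assumed values of f and on borrowing the plan's rates for month 6. If late viewing has no effect, there is no dilution. In a pilot with a standard error of about 13 points, a moderate loss would be hard to see, but it would be systematic and avoidable. The stated 52 per arm and the month 1 to 3 comparisons are not called into question.

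**What to change.** In Specific Aim 3 of both Protocol and SAP, take the effect size at the 3-month post-quit assessment, before the videos are released, using the outcome collected there: 7-day point-prevalence abstinence with cotinine confirmation. Limit the hypothesis in the Project Description to 3 months. Add a sentence that no between-arm estimate after release will be reported as the SNC effect.

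This changes text only and needs no further participants or procedures. Its price is that the pilot gives no 6-month effect size.

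If the sponsor prefers to keep month 6, release to controls has to move to after that assessment, in both Research Design and Video Watching. That is more than rewording: it needs an added visit with its test kits, incentives and retention effort, and controls would wait about three months longer for the videos.

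As a minor clarification, reconcile the two statements on when cotinine kits arrive, and state that release follows completion of the month-3 cotinine test where one is due. The wait for controls would be a few days at most.

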2. Phase 2. An RCT of a Storytelling Narrative Communication Intervention: Counseling contents will be primarily drawn from a cognitive behavioral therapy foundation, which is guided by Bandura's Social Cognitive Theory.^{33,34} Within the theory, self-efficacy, that is, the conviction that one can successfully execute a behavior required to produce the outcome is viewed as the most influential determinant of the behavior and its appraisals are based on the following four: performance accomplishment, vicarious experience, verbal persuasion, and physiological state. Participants will have eight weekly counseling sessions and the duration of the sessions is approximately 200-240 minutes over 8 weeks. They will be counseled to enact small changes that are accomplishable, which will be the source of performance accomplishment. Both HIV-tailored and SNC interventions will augment self-efficacy via vicarious experience and verbal persuasion. The NRT will further increase self-efficacy by targeting physiological state. To prevent attrition, we will execute several strategies, including tracking subjects at least every month and providing incentives for follow-up tests. Counselors will proactively call participants prior to each therapy session and confirm the appointment a few hours before the session. A research assistant (RA) will conduct all follow-up assessments via telephone calls and video call for saliva cotinine tests. Regardless of smoking status, participants will receive a Visa gift card worth \$25 at each follow-up assessment (post-quit 1, 2, and 3 months). Any participants who report abstinence at post-quit 3 months will be asked to do the salivary cotinine test via a video call on a smartphone and receive another Visa gift card worth \$25 upon completion of the test. Those who complete all three follow-up assessments will receive one time bonus of a gift card worth \$100.

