8. Have at least eight full drops of saliva drip from the tube onto the white padded area of the test strip (right below the three green arrows).

A research staff member will closely monitor the whole process via the video call. She/he will be blind to treatment condition. The person can read the result of the test when the blue line on top of the strip disappears, which usually takes 20-30 minutes. She/he will ask participants to take a photo of the strip right after the video call and send it to her/him. Then, the person will share the photo with other research staff to validate one's reading of the result.

Study Measures and Assessment Procedures: Baseline and three follow-up assessments will be conducted by telephone survey. All measures (see Table 1 below) have been tested and validated for use with WLHIV. Those who report abstinence will receive NicAlert® test kits at 3-month follow-up by a post office mail right before the follow-up assessments. As described above, participants will be guided step-by-step to perform the test while the whole process being closely monitored by research staff via a video call.

Table 1 Assessment schedule of study measures

Variables	Measure	Base	1M*	2 Ms*	3 Ms*
Demographics	Demographic Datasheet	✓			
History of HIV Infection	Year of the diagnosis, CD4 cell count, and viral load	✓			
HIV-medication Adherence	CASE Medication Adherence Scale ⁴⁰	✓			
History of Smoking and Quitting	Smoking and Quitting Datasheet	✓			
Stigma and Secrecy	HIV-related Stigma Scale ⁴¹	✓			
Alcohol Use	Alcohol Use Disorders Identification Test (AUDIT) ³²	✓			
Depression	Patient Health Questionnaire-9 ⁴²	✓			✓
Anxiety	Generalized Anxiety Scale-7 ⁴³	✓			✓
Nicotine Dependence	Fagerström Test for Nicotine Dependence ^{37,38}	✓	✓	✓	✓
Self-Efficacy	Self-Efficacy Scale ⁴⁴	✓	✓	✓	✓
Nicotine Withdrawal	Minnesota Tobacco Withdrawal Scale ³⁶		✓	✓	✓
Narrative Engagement	The Measure of Narrative Engagement ¹⁹			✓	✓
Program Evaluation	The Client Satisfaction Questionnaire ⁴⁵		✓	✓	✓
Abstinence or Cigarette Consumption	7-day Timeline Follow-back Smoking Behavior ³⁵		✓	✓	✓
	Saliva Cotinine Test (NicAlert®)				✓
Treatment Fidelity	Intervention Fidelity and Competence Scale ([name], unpublished work)		✓	✓	✓

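### The cotinine assessor is said to be blind, but the same research assistant role also runs telephone surveys that include video-related measures, with no safeguard described, so the blinding is likely to be compromised from month 2

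*Protocol*

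**What the plan says.** In the Protocol, Saliva Cotinine Test, a staff member watches the home test by video call, and the text says: "She/he will be blind to treatment condition". The participant then photographs the strip, and the photograph goes to other staff as a check on the reading.

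Under Study Procedures, Phase 2, the work is assigned as follows: "A research assistant (RA) will conduct all follow-up assessments via telephone calls and video call for saliva cotinine tests". Under Study Measures and Assessment Procedures: "Baseline and three follow-up assessments will be conducted by telephone survey".

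Table 1 ticks "The Measure of Narrative Engagement" at 2 and 3 months. It ticks the satisfaction questionnaire and the 7-day smoking self-report at 1, 2 and 3 months, and the cotinine test at 3 months only.

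Under Video Watching, women will, according to arm, "receive the videos of either quitting smoking or being diagnosed with HIV infection, respectively". Controls get the quitting videos only "right after the last data collection that is 3-month follow-up post-quit".

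Specific Aim 2, worded alike in the Protocol and the SAP, adds an exit survey and this rating: "They will also rate their experience with the SNC videos, using a 7-point Likert-type scale". Specific Aim 3 counts as smoking any woman who cannot be reached or whose cotinine result is above the cutoff. The SAP text says nothing about blinding.

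**The concern.** The video is what separates the arms, so to learn which video a woman watched is to learn her arm. The plan has the same role talk with women by telephone about their engagement with a video and then take, or verify, their smoking status. An assistant who has learned the arm may, without intending to, probe smoking harder in one arm, try harder to reach women in one arm, or lean one way on a faint strip.

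This matters because a stated aim is to establish an effect size for later grant applications. A reader who trusts the blinding statement would give that estimate more credit than the described procedures support.

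**Working it through.** **1. Who does what.** Saliva Cotinine Test describes a blind staff member. Study Procedures, Phase 2, names the research assistant as the role that makes the cotinine call and conducts all follow-ups. Read together, the person declared blind holds the same role as the interviewer.

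**2. What that role hears before the strip is read.** The Protocol gives two times for mailing the kit. Saliva Cotinine Test has it sent after abstinence is reported at month 3, arriving in 2 to 3 days. Study Measures and Assessment Procedures has it mailed shortly before the follow-up. On the former timing, the month-3 interview comes before the test. On either timing, the month-2 interview, which includes the narrative engagement measure, comes before it.

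**3. Whether that conversation can identify the arm.** One arm saw stories about quitting and the other saw stories about an HIV diagnosis. Even a neutrally worded question leaves the answer free: a woman describing her involvement in a story can easily name its subject.

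**4. Safeguards.** I looked for a separate interviewer for the video items, a self-completed form, a fixed order of items, an instruction to participants, and a statement that the second photo reader is blind. The documents describe none of these.

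**5. Where the exposure falls** (from Table 1, Saliva Cotinine Test and Specific Aim 3).

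| | Month 1 | Month 2 | Month 3 |
|---|---|---|---|
| Items that may touch on the video | satisfaction only | narrative engagement, satisfaction | narrative engagement, satisfaction |
| Abstinence measure | self-report | self-report | self-report, then cotinine if abstinence is reported |
| Blinding stated | no | no | for the test monitor only |
| Check on the measure | none | none | cotinine for reported abstinence; photo and second reading for the strip |

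At month 2 the self-report stands alone. At month 3 it decides who is tested, so the test can overturn a report of abstinence but not a report of smoking.

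**6. Scale.** No figure in the plan bears directly on blinding. The yardstick is the planning difference in Power and Sample Size, 45.5% − 20% = 25.5 points. The sample size built on it reproduces. With the pooled normal approximation, two-sided 5%, 80% power and p̄ = (0.455 + 0.20)/2 = 0.3275:

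n = [1.96·√(2·0.3275·0.6725) + 0.8416·√(0.455·0.545 + 0.20·0.80)]² / 0.255² ≈ 52 per arm, as stated.

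With the planned 25 per arm:
- one woman classified differently moves her arm's rate by 1/25 = 4 points;
- one in each arm, in opposite directions, moves the difference by 4 + 4 = 8 points;
- 8/25.5 = 0.31 of the planning difference.

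This shows how sensitive a trial of this size is to any classification error. It says nothing about how likely such errors are here.

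**The case against.** A reader might infer that the blinding cannot hold, because whoever asks these questions must learn the arm. The documents do not support that, for four reasons.

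- **Item wording is not given.** Both arms receive three short videos at the same monthly interval. Table 1 schedules narrative engagement without restriction by arm, and its four dimensions (comprehension, attention, presence and emotional involvement) are neutral as to content. The same items could be asked in both arms about the video she saw.
- **The rating that names the SNC videos is not shown to be the assistant's task.** It appears beside an exit survey that participants complete. Neither is listed by name in Table 1, and their administrator and timing are not stated. The rating could follow all smoking data.
- **The assistant is a role.** Other sentences speak of research staff in general, so several people may fill it.
- **The blinding statement is limited.** It covers only the person handling the cotinine test, and for that step the photograph and second reading already reduce the risk. Month 1 has no narrative measure.

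All four stand as limits on the claim, but they do not remove it. Neutral questions do not control what an unblinded woman says in reply. Several assistants would protect the blinding only if whoever reads the strip had not held the narrative interview, and no such division is described. The narrow reach of the statement also leaves the more exposed measure, the self-report, with no stated blinding at all.

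**Conclusion.** The point holds in limited form. The Protocol states blinding for the cotinine test, gives the test and the video-related telephone surveys to one role, and describes nothing to keep that role from learning the arm. The blinding is unprotected and likely to be compromised from month 2 on; that it must fail is not shown.

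Exposure is greatest for the 7-day self-report at months 2 and 3 and smaller for the strip reading. Effort to reach women is also exposed, because those not reached count as smoking. Size and direction of any bias cannot be derived from the documents; the 4 and 8 points are scale only.

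The conclusion assumes that Table 1's narrative engagement measure is part of the assistant's telephone survey, as the text around the table indicates, and that no unstated division of calls exists. It is a correctable weakness, not a fatal one.

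**What to change.** - At each follow-up, take the smoking report before anything else and record it before any other item is asked.
- Remove the narrative engagement, satisfaction and SNC-video ratings from the assistant's call. Collect them by self-completed text or web form that the assessor does not see. Do not route them through the counsellor, to whom women may give favourable ratings.
- State that the second reader sees strip photographs without arm labels.
- Ask participants not to mention their video to the assessor.
- Reconcile the two kit-mailing times, so that the order of self-report, test and video items is fixed and the same for all women. If video items simply waited for the strip result while kits took 2 to 3 days to arrive, they would be delayed for women reporting abstinence only.

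If these changes are not made, remove the blinding statement.

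The cost is small: questionnaires move to another mode and no staff are added. The downside is that some self-completed forms may be missing, which would affect the acceptability measures of Specific Aim 2 but not the abstinence outcome.
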